Data quality will be ensured through making the questions in the web-based surveys, IVR and clinical interviews in the study as clear as possible, primarily through use of established measures that have been determined to be reliable and valid. On the web survey, respondents will review a brief summary emphasizing the importance of providing honest and valid responses while completing the survey. They will also be encouraged to respond to the survey only once and discouraged from providing invalid contact information. This will increase the likelihood that participants will give valid responses. All research staff will be carefully trained by the Principal Investigator. Drs. [name] and [name], who are experienced data analysts, will be primarily responsible for conducting the preliminary and final data analyses with advice from collaborators and with support from [name].

Right to privacy for participation in this research will be protected through coding of data using study-assigned identification numbers and proper storage of research records. Access will be limited to the P.I. and his designates involved in the study. Hard copy master lists linking study IDs to research participants' contact information will be stored in locked cabinets at the Yon Hall research facility and in [name] office in Florida Gymnasium. These lists will be stored separately from other study materials. Identifiers will be destroyed when the study is completed. All email contact with participants will occur with the use of secure UF email accounts only. Web-based data collection will be encrypted and stored on secure servers, but will not contain any identifiers other than study ID and in the case of the web survey, IP address. A Certificate of Confidentiality has been obtained from NIAAA for this study. This certificate protects the confidentiality of all research records generated by this study. Individually identifiable health information will be protected in accordance with the Health Insurance Portability and Accountability Act of 1996. All research and medical personnel will be trained on human subjects' protection and HIPAA procedures.

Clinicaltrials.gov requirements. This study will be registered on clinicaltrials.gov.

References

1. Carey, K.B., L. A. Scott-Sheldon, M.P. Carey, and K.S. DeMartini, Individual-level interventions to reduce college student drinking: A meta-analytic review. *Addictive Behaviors* **32**, 2469-94 (2007).

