IVR: Cumulative personalized normative feedback will be generated weekly based on IVR responses. Similar to the web component, participants will get feedback with text and graphs on 1) drinks per week compared to normative data; 2) days with protected/unprotected sex compared to normative data; 3) number of days taking medication/completing other health activity; 4) comparisons between instances of sex (protected/unprotected) following alcohol versus not; and 5) medication taking/other health activity on drinking vs. non-drinking days. Feedback will be mailed to a postal address or posted to a secure, password-protected webpage.

Focus Group.

Sources of materials: Research data are derived from the on-line questionnaires as in the web survey and from discussion about the web-based alcohol and HIV intervention component during the focus groups. Discussion will be recorded using an electronic recording device and later transcribed verbatim, hard copies of which will be reviewed by study staff. All data are obtained strictly for research purposes and with the informed consent of subject participants, and are confidential.

In-person focus group: Participants who are selected randomly from among web-survey completers in the Gainesville area or recruited locally will be invited to take part in a focus group. These sessions will take place either in Yon Hall North or Florida Gymnasium on the UF campus. The Florida Gym and Yon Hall North facilities are centrally located on campus, both

connected to Ben Hill Griffin Stadium. These research facilities have dedicated, free parking for research participants. With the convenient location and parking, the research facilities are also readily accessible by emergency personnel in the unlikely event of an emergency. Focus group sessions will last about two hours. Compensation will be \$35. Written informed consent will be obtained at the outset of the appointment.

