30-day intervention period: Participants will be asked to complete assessments using the IVR system daily for a 30-day period. The IVR system will call up to 3 times/day using the number provided by the participant until successful. Participants can also call back at a dedicated phone number using a personalized code. The 5-minute assessment will include items on alcohol, sex and medication taking. Given PrEP is not included, participants will report on another medication or health activity. Staff will remind by phone or text message if they miss a day. Based on the participant's IVR responses, study staff will produce a cumulative personalized feedback document that will be posted to a secure site on the web to which only that study participant will have access, or it will be mailed to the participant's postal address, based on their preference.

Follow-up appointment: After the end of the 30 day IVR field period, participants will return for a follow-up appointment. At this appointment, they will complete another web-based TLFB assessment and repeat the rest of the measures from baseline. They will also be asked to give their views on each component of the intervention including how much they liked using it; how

useful they believe each part was in prompting them to change their behaviors and to offer suggestions for improvement, particularly ways to enhance the appropriateness of the intervention components for young adult MSM.

Assessments. On the pre-screen to indicate eligibility for the full survey, participants will be asked demographics (birth sex, age range); number of instances of intercourse in the past 3 months with same and opposite sex partners; HIV status and whether have taken PrEP. The following will be included in the full survey:

Demographics: The full survey includes questions on age, race, ethnicity, highest educational attainment, employment type, marital status, personal and household income.

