Alcohol/substance use & sexual activity: Participants will complete an online TLFB⁸¹ covering past-month alcohol and other substance use, adapted to include sexual activity^{20,87}. Participants record memorable anchor events on calendars that serve as recall aids, then report daily drinking of beer, wine, and liquor and use of licit and illicit substances⁸⁸. Participants report daily instances of sexual activity including whether day-to-day activity was with the same or different partners. On days when they indicate activity, they will be asked whether the partner was same or opposite sex, whether protection was used, and number of drinks before sex.

Sexual risk behaviors: The reliable and valid sexual risk subscale of the RAB⁸⁶ will be used, which contains 8 items each with 4 response options addressing sexual behaviors over the past 6 months.

Perceived HIV risk: The PRHS⁸⁵ is a reliable and valid 8-item measure of perceived risk of HIV infection that captures likelihood estimates, intuitive judgments and salience of risk.

HIV testing history. Participants will be asked to report the number of times they have taken any type of HIV test in the past 12 months and in their lifetimes.

Sexually transmitted infection history items: Participants will be asked to report regarding whether they have been diagnosed with 4 types of STIs in the past 12 months or prior.

Hazardous drinking: The Alcohol Use Disorders Identification Test* (AUDIT⁸³) is an established, 10-item scale including items on alcohol use and DSM-IV dependence criteria that has been used in college samples^{90,91}.

Protective behavioral strategy use: The revised Protective Strategies Questionnaire (PSQ) contains 11 direct and indirect protective behavioral strategies. Participants rate the extent to which they use each on a 7-point scale. Additional items will be added to extend measurement of protective strategies to avoid additional alcohol-related sexual harms. In addition to the aforementioned questions, additional questions also on 7-point scales will ask participants about their openness to using each of the 16 strategies in the future.

PrEP knowledge and attitudes: These items will be taken from Co-Investigator [name] Cohort study. Participants will report whether they have heard of PrEP and openness to future use. On 5-point scales, those who have heard of PrEP will report perceptions of its safety, effectiveness, and difficulty in taking it daily.

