Motivation: On 100-point visual analog scales, participants will report their interest in immediately making the following behavior changes: drinking less alcohol; quitting alcohol use altogether; having less sexual activity altogether; having less unprotected sexual activity; having sex less frequently following alcohol/substance use.

The *UPPS Impulsive Behavior Scale*^{92,93} is a reliable, valid 59-item measure that assesses 5 subdimensions of impulsivity (premeditation, positive urgency, negative urgency, sensation seeking and perseverance).

Measures for usability study: The same assessments will be administered at baseline and conclusion of the 1-month usability study. In addition, usability study participants will be asked their liking of the intervention and agreement it is useful on 7-point scales and there will be an open-ended item where they can provide written input. Usability study participants will also complete the following assessments via the IVR system:

IVR assessment: Questions will concern behaviors the preceding day. Similar to [name] et al.^{20,61}, participants will report number of drinks; whether they used a substance other than alcohol to get high; and whether they had sexual activity. If they reply “yes,” follow-up questions will ask whether it was with a same or opposite sex partner; with their main, non-main or anonymous partner; type of activity (anal, oral, vaginal); whether or not protection was used; and whether or not a transaction for money or goods was involved. For those reporting alcohol or other substance use and sexual activity, a follow-up question will ask if substance use occurred before or after sex. The IVR system will include a question on PrEP use though usability study participants will respond according to another medication or health behavior. TLFB⁸¹ will provide data for missing IVR days.

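### The IVR call as described cannot correctly fill the weekly feedback element on protected and unprotected sex after alcohol on every day with sex, because its one timing question pools alcohol with other substances

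*Combined protocol and SAP*

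**What the plan says.** **What the feedback must show.** In the protocol's Research Plan, under the intervention description (IVR paragraph), "Cumulative personalized normative feedback will be generated weekly based on IVR responses". Five elements follow. The second is "days with protected/unprotected sex compared to normative data" and the fourth is "comparisons between instances of sex (protected/unprotected) following alcohol versus not". The Usability Study section (30-day intervention period) repeats that staff build the feedback document from the participant's IVR responses.

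**What the call collects.** Under Assessments (IVR assessment), each call covers the preceding day. Participants give a number of drinks, then "whether they used a substance other than alcohol to get high; and whether they had sexual activity". If there was sex, follow-ups include one on whether protection was used. There is one timing question: "For those reporting alcohol or other substance use and sexual activity, a follow-up question will ask if substance use occurred before or after sex".

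**What the TLFB collects.** Under Assessments (alcohol/substance use and sexual activity), on days with sex the TLFB asks "whether protection was used, and number of drinks before sex". On its timing, the Usability Study section says: "After the end of the 30 day IVR field period, participants will return for a follow-up appointment". It continues: "At this appointment, they will complete another web-based TLFB assessment and repeat the rest of the measures from baseline". The IVR assessment paragraph gives the TLFB the role of supplying data for missing IVR days.

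**The concern.** The fourth element needs two facts about each occasion of sex: whether protection was used, and whether alcohol came first. The call asks about alcohol and other substances separately when it measures use, then merges them when it asks about timing. It also asks about sex as yes or no for the day, while the element is worded in instances.

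This is the only one of the five IVR feedback elements that sets drinking against protected and unprotected sex, and the project's goal is to reduce alcohol use and risky sex together. If a day is put in the wrong cell, a participant could be told that sex followed drinking when it did not, or the reverse. Because the feedback is cumulative, a misplaced day would carry into his later reports. The staff who prepare the document have no stated rule for such days.

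**Working it through.** The plan gives no figure on this point and no arithmetic applies. The check is whether the call items, as described, settle the fourth element on each kind of day with sex.

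**Days with one occasion of sex.** Protection is taken directly from the protection follow-up. That leaves whether alcohol came first.

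1. *No alcohol, no other substance.* The drink count is zero, so sex did not follow alcohol. Settled.
2. *Another substance only.* The drink count is again zero, so whatever the timing answer, sex did not follow alcohol. Settled.
3. *Alcohol only.* The timing answer can refer only to alcohol. If drinking was wholly before or wholly after sex, the answer settles it. If he drank both before and after, the before-or-after question has no stated answer for him. Should he answer *after*, the day is filed as sex not following alcohol although it did. Unless a rule says that any drinking beforehand counts as *before*, an *after* answer is therefore not safe.
4. *Alcohol and another substance.* Suppose one preceded sex and the other followed it. The text does not say how to answer.
   - If *before* means that any substance came first, a *before* answer fits a man who drank first and also a man whose other substance came first and who drank only afterwards. The fourth element differs between the two. An *after* answer would be settled.
   - If *after* means that any substance came later, the open answer is *after* instead, and *before* is settled.
   - If the choice is left to the caller, which is all the text supports, neither answer settles the day.

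**Days with more than one occasion of sex.** The call as described gives one yes/no on sex, one answer on protection and one on timing. The number of instances is not recorded. If the acts differed in protection or in preceding alcohol, single answers cannot be divided among them. If the acts did not differ, a day-level version of the element loses nothing.

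**Whether another source fills the gap in time.** The TLFB asks specifically about drinks before sex. The TLFB that covers the IVR days is completed after the 30-day period, whereas the reports are weekly. Its stated role is also to supply missing IVR days, not to correct completed ones. The baseline TLFB covers the month before the calls began. Neither can feed the weekly document. Only the TLFB's alcohol-specific wording is relied on here, since its protection and drinking details are also described by day.

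**Unit.** The second and fourth elements sit in the same list, one in days and the other in instances. The daily yes/no item supports the first unit and not the second.

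**The case against.** The strongest reply is that the IVR paragraph is a short prose summary, modelled on earlier cited work, and the call script is not in the document. The timing sentence could mean that the question is asked for whichever substance was reported. That is possible, and it limits the point to the call as described. It does not remove it, because the text names pooled substance use and nothing elsewhere separates alcohol.

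A second reply is that an instance may simply mean a day with sex. On that reading the count gap largely closes and what remains is a mismatch of wording with the second element. This reply mostly stands. It leaves the pooled timing question untouched.

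A third is that the plan has its own correction path: staff testing of the IVR in months 1-6, a usability study whose aim includes correcting functionality issues, and further IVR changes afterwards. That limits the consequence. It would not necessarily reveal the problem, because a misfiled day produces no visible fault.

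A reader might also infer that the fourth element cannot be derived at all. The documents do not support that: one-occasion days without alcohol are settled, as are alcohol-only days on which all drinking fell on one side of sex. Nor can one list the possible answer patterns and read the open ones as a proportion of days. The patterns are not equally common, their number depends on how *before* and *after* are read, and the documents give no rate of co-use days or multi-act days.

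**Conclusion.** The point holds as a minor one. As the call is described, the fourth weekly feedback element cannot be derived correctly on every day with sex. The exposed days are those with both alcohol and another substance, alcohol-only days with drinking on both sides of sex, and days whose acts differed.

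The share of days affected is unknown. The reach is one of five descriptive feedback elements in an uncontrolled usability study of 10 men. A reader might infer that the study's results or size are undermined. They are not: no hypothesis test, sample size or error rate depends on this element.

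The conclusion assumes that the programmed call matches the protocol's description, with one pooled timing question and no repeat for each act. If the script already asks alcohol timing separately, the main part becomes a matter of description only.

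**What to change.** Make two changes before the usability study.

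1. When the drink count is above 0 and sex is reported, ask timing for alcohol on its own. Reuse the TLFB item on drinks before sex, scored 0 versus 1 or more. This settles co-use days, and also days with drinking on both sides of sex, since any drink beforehand counts.
2. Restate the fourth element in days with sex, matching the second. Show days whose acts differed in protection or in preceding drinking as a separate *mixed* category. To identify those days, the protection and alcohol-timing items need a response for *differed between occasions*.

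Mixed days should not be assigned to the unprotected, after-alcohol cell. Take a day with one unprotected act before any drinking and one protected act after drinking. Assigning it there would tell the participant of a link between drinking and unprotected sex that did not occur.

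The cost is one alcohol-only timing item, an added response option, and a wording change to the fourth element. The call, planned at 5 minutes, lengthens by a few seconds on affected days, and the act-level comparison is given up. If the script already asks alcohol timing separately, a sentence saying so in the IVR assessment paragraph replaces the first change.
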